7.3.2 Handling of missing data in active subjects	31
8. Safety analysis	32
8.1 Summary of adverse events.....	32
8.1.1 Number of adverse events.....	32
8.1.2 Number of patients affected by an adverse event	32
8.2 Analysis of adverse events	32
8.3 Summary of Serious Adverse Events (SAE).....	32
8.4 Analysis of SAE	33
9. Presentation of analysis	33
9.1 Reporting of results.....	33
9.2 Presentation of results	34
10. References, related SOPs, web links.....	34
11. Appendices and associated documents	35

Abbreviations

AE	Adverse Event
BE	Barrett's oEsophagus
BMI	Body Mass Index
BOC	Benign Oesophageal Condition
CLR	CLuster Randomised
CRF	Case Report Form
DMC	Data Monitoring Committee
EAC	Oesophageal AdenoCarcinoma
GI	GastroIntestinal
GP	General Practitioner
H2RA	Histamine-2 Receptor Antagonists
IM	Intestinal Metaplasia
IQR	Interquartile Range
ITT	Intention-To-Treat
MHRA	Medicines and Healthcare products Regulatory Agency
NHS	National Health Service
NPV	Negative Predictive Value
OGD	Oesophago-Gastro-Duodenoscopy
PLR	Patient-Level Randomised
PPV	Positive Predictive Value
RCT	Randomised Controlled Trial
SAE	Serious Adverse Event
SAP	Statistical Analysis Plan
STAI	Spielberger State-Trait Anxiety Inventory
TFF3	Trefoil Factor 3
VIF	Variance Inflation Factor

1. Purpose and objective

This document contains the **Statistical Analysis Plan (SAP)** for the BEST3 study. The SAP is required by the National Institute of Health to improve reproducibility, transparency and validity of clinical trials.

The table of contents of this SAP follows the one recommended in SOP Barts CTU GEN ST 01 “Statistical Analysis Plan”, version 4.0.

[figure not shown]
2. Study objectives and design

The BEST3 study is a 1:1 randomised controlled trial (RCT) where consented patients are either recruited to usual care or to receive an invitation to the **Cytosponge™-Trefoil Factor 3 (TFF3)** test, a novel non-endoscopic device whose purpose is to detect Barrett’s oEsophagus (BE), a pre-cancerous lesion of oesophageal cancer.

Subjects recruited in the BEST3 study are either cluster randomised (CLR), i.e. General Practitioner (GP) practices are the units of randomisation, or ‘patient-level’ randomised (PLR), i.e. patients are individually randomised to either the intervention or the control arm. This second type of randomisation was added to the study at a later time because of concerns in low recruitment numbers and it was allowed by the fact that some initial conditions of the study were not holding anymore (e.g. GPs were initially expected to recruit patients on an individual basis as they presented, but this was later substituted with automated searches in practice records). Subjects recruited in a PLR fashion confer greater power to the study. For more information on this amendment, see:

<G:\EMS\CPTU\BEST3\Section 6 APPROVALS AND AUTHORISATIONS\8. Amendments\Amendment 6>

Figure 1. Trial flowchart

2.1 Primary endpoint

The main aim of the trial is to compare the numbers of histologically **confirmed BE diagnoses** between the two study arms. This will confirm whether the Cytosponge™ detects more BE than the current practice (i.e. GP referring a patient to endoscopy).

2.2 Secondary endpoints

To be assessed using data from the intervention arm *only*:

- 1) Diagnostic accuracy of Cytosponge™
- 2) Performance of Cytosponge™ in detecting severity of BE
- 3) Performance of Cytosponge™ in detecting intestinal metaplasia (IM) of the gastric cardia: based on IM detection by endoscopy of Cytosponge™-positive patients without BE
- 4) Performance of Cytosponge™ in detecting BE or IM of the gastric cardia
- 5) Performance of Cytosponge™ in detecting oesophageal adenocarcinoma (EAC) and gastric cancer
- 6) Sampling adequacy
- 7) Endoscopy referral rates for adequate test results and successful Cytosponge™ swallows
- 8) Patient acceptability of Cytosponge™: willingness to have the test and to have a repeat procedure, number of patients who fail to swallow, cancer worry, long-term emotional or physical harm, perceived risk of EAC, test experience.
- 9) Physician/nurse acceptability of Cytosponge™
- 10) Safety of Cytosponge™
- 11) Performance of repeat Cytosponge™ test

To be assessed using data from the usual care or *both* study arms:

- 12) Number of BE diagnoses missed in the current management
- 13) Number of undiagnosed BE in the general population vs in the group who received Cytosponge™
- 14) Prevalence and incidence of benign oesophageal conditions (BOCs)
- 15) Acceptability of endoscopy
- 16) Number of BE diagnoses for patients with a negative Cytosponge™ result
- 17) Quality control of endoscopic and pathology results

Epidemiological and longer-term objectives (for up to 10 years):

- 18) Prevalence and incidence of BE during the study
- 19) Prevalence and incidence of BE with dysplasia during the study
- 20) Prevalence and incidence of EAC during the study
- 21) Prevalence and incidence of IM and related gastric cancers during the study
- 22) Prevalence and incidence of BE up to 10 years after the study
- 23) Prevalence and incidence of BE with dysplasia up to 10 years after the study

- 24) Prevalence and incidence of EAC up to 10 years after the study
- 25) Prevalence and incidence of IM and related gastric cancers up to 10 years after the study
- 26) Research and development: Genetic and biochemical risk factors for disease progression (germline and somatic variants and other biomarkers) including targeted, exome level and whole genome sequencing

Health economics analysis:

- 27) To undertake modelling to predict the reduction in EAC-related mortality from this strategy (short and long term)
- 28) Cost of the Cytosponge™ test versus usual care
- 29) Cost-effectiveness of the Cytosponge™ versus usual care

2.3 Assessment of objectives

Assessment of primary endpoint

To assess the primary endpoint, research endoscopy findings (after the end of the follow-up period) will not be taken into account.

Because of the nature of the study, only participants who accepted the invitation to the Cytosponge™ test gave consent to the use of their data for study purposes. In order to collect primary endpoint data in consented Cytosponge™ patients, non-responders of the invitation and usual care participants, at least one of the following different data sources will be used:

- 1) **Automated coded search** for BEs, OGDs, EACs or upper gastrointestinal (GI) referrals: carried out on the GP electronic clinical records for all participants in all sites.
- 2) **Manual case-note review** of the GP clinical record for all participants identified by the coded search plus a number of other participants depending on the capacity of the sites: some practices will include all participants, some will include no additional participants and others will perform a manual review on a sample of participants chosen at random by the Trial statistician.
- 3) **National Health Service (NHS) number linkage** with hospital records for a limited number of sites, depending on the availability of relevant hospital information systems that routinely capture relevant diagnoses and geographical proximity of site in relation to its linked hospital.
Note: NHS number linkage will not be performed for all hospitals. For instance, in London, this step may be forgone because of the high population density and the consequent difficulty in determining the hospital catchment of sites.

Automated coded searches will be run by the study sites. The central study team does not provide the practices with the codes as different codes are in use in different practices. Following this step, the sites will fill in a spreadsheet prepared by the Trial team asking for the following information by sex and 10-year age range (50-59, 60-69, 70-79, 80-89, 90+): type of upper GI referrals and investigations; upper GI diagnoses during follow-up; treatment for BE. PLR sites will be asked to fill in two different spreadsheets, one for their usual care and one for their intervention patients. They will also indicate in the online database how many endoscopy referrals, BEs and adenocarcinomas (and the affected patients) they will have found in their records.

Manual case-note reviews consist of checking a patient’s record closely and filling in an electronic database form with information on: length of follow-up, sex, age range, body mass index (BMI) range, smoking history, drinking history, GP consultations, type and length of acid-suppressant medications, Helicobacter pylori course, aspirin course, medication review, symptoms, any diagnosis following Cytosponge™ test, any treatment for BE.

For NHS linkage, the encrypted NHS numbers of all participants will be sent by practices and NHS numbers of all new diagnoses of BE will be sent by participating endoscopy units to Cambridge University (the “Trusted Third Party”) for anonymous matching. NHS numbers will be scrambled using a one-way hashing system (to a SHA256 standard), so will be not identifiable to anyone outside the practice. Sites (GP practices and endoscopy units) will receive an Excel macro tool to perform the encryption. Any endoscopic diagnoses found through this method will be checked directly with the study sites. This step has received approvals from the NHS Research Ethics Committee as part of Amendment 6 to the BEST3 Protocol.

Where there is evidence of endoscopy from one of these sources, further details may be sought from clinical records. Study-related endoscopies for participants with positive or other relevant Cytosponge™ results will be used for this purpose.

Note: it is important to record the date up to which the coded search is looking for BE and OGDs/EACs/upper GI referrals. This date should be used as the date of last follow-up for that patient, i.e. any BE diagnosed after that date should not be included in the primary endpoint.

Table 1: A schematic of how Methods 1 and 2 work together.

SECOND STEP: manual case-note review returns...			
	BE diagnosis	Negative	Not done
FIRST STEP: automated coded search returns...	BE diagnosis	For all patients with a BE diagnosis picked up in the coded search	N/A
	OGDs/EAC/referral	Some of the patients with an OGD/EAC/referral will have a BE diagnosis when their record is reviewed.	Some of the patients with an OGD/EAC/referral will not have any BE diagnoses when their record is reviewed.
	Negative	A randomly selected number of patients who have not been identified by the coded search will have their records reviewed, which will show a BE diagnosis.	A randomly selected number of patients who have not been identified by the coded search will have their records reviewed and no BE diagnoses will be found.
			N/A
			Most patients not identified by the coded search will not have their records reviewed manually.

The primary endpoint will be histological confirmed BE (column “BE diagnosis” in Table 1 plus any BEs picked up by the NHS number linkage exercise) only. (The case-note review should make clear where the BE was confirmed on histology or whether it was just the impression on endoscopic that was not confirmed.) Patients with BE identified via any of the three routes (automated search plus manual confirmation, manual search, record linkage) will be considered to have BE. Patients whose records have not been searched by any of the three approaches will be considered to have missing BE status. All other patients will be considered not to have a BE diagnosis. All patients with a BE/OGD/EAC/upper GI referral should have a manual review to confirm the diagnosis; if they have not had a manual review, their BE status will be considered as (partially) missing and handled through multiple imputations (of the outcome of the missing review).

Approximate balance in the number of full case-note reviews performed at random should be ensured between the two arms for practices in the CLR group.

Important! BEs known to the study team but not identified through at least one of the three methods describes above will not count towards the primary endpoint analysis. This is most likely to apply to cases detected following a positive Cytosponge™-TFF3 stain and resulting in an endoscopy performed by a study gastroenterologist. This rule is to ensure that the same data collection methods are used in the two study arms (as trial endoscopies are not available in the usual care arm) and helps avoid any biases. However, as a sensitivity analysis, all BEs known to the study team (prior to the exit research endoscopies) will be included. . For statistics relating only to the Cytosponge™ (e.g. PPV of the TFF3 stain), all cases of BE will be included.

Assessment of secondary endpoints

To be assessed using data from the intervention arm *only* (include all BE regardless of the route of study ascertainment):

- 1) Diagnostic accuracy of Cytosponge™ according to endoscopic findings only (focus: length of BE)
 - Positive Predictive Value (PPV) = proportion of patients with positive Cytosponge™ test result who have a confirmed BE diagnosis following endoscopy
 - PPV by length of BE detected (length of BE categories: >= C1, >= C2, >= C3)
 - Negative Predictive Value (NPV) = proportion of patients with negative Cytosponge™ test result receiving a research endoscopy after the end of the follow-up period who have a confirmed diagnosis of no BE
- 2) Performance of Cytosponge™ in detecting severity of BE, i.e. diagnostic accuracy of the test according to endoscopic and pathology findings
 - PPV of the test by severity of BE (except for score = 0)

Severity of BE for positive Cytosponge™ patients will be scored after biopsy according to the following table:

Score	BE severity
0	Pathology report not available

1	IM of oesophagus on biopsy and endoscopic findings not seen in categories below
2	C1 or C0 up to M3 + IM
3	C2 or more, C0 M4 or more + IM
4	C3 or more
5	Low grade dysplasia (LGD)
6	High grade dysplasia (HGD) or T1a cancer

- 3) Performance of Cytosponge™ in detecting IM of the gastric cardia:
 - PPV of the test for detection of IM of the gastric cardia in patients without BE, i.e. BE with IM will be excluded
- 4) Performance of Cytosponge™ in detecting BE or IM of the gastric cardia:
 - PPV of the test for detection of BE or IM of the gastric cardia, i.e. patients from endpoints 1) and 3) combined
- 5) Performance of Cytosponge™ in detecting EAC and gastric cancer:
 - PPV of the test for detecting EAC or gastric cancer
- 6) Sampling adequacy (for first test, and first and repeat test combined):

An *adequate* result is defined as: high-confidence negative (squamous and glandular cells), low-confidence positive (squamous and glandular cells with IM), or high-confidence positive (squamous and glandular cells with IM or cellular atypia).

An *inadequate* result is defined as: processing/technical failure, low-confidence negative (squamous cells only), or equivocal (squamous and glandular cells with equivocal TFF3 staining).

Sampling adequacy will be reported for the following measures for first test, and then for first and repeat test combined (i.e. not considering the result of the first test for those patients having a repeat test):

- Inadequacy rate = proportion of Cytosponge™ test results that are deemed insufficient/inadequate due to processing or technical failure, low-confidence negative (squamous cells only) or equivocal (squamous and glandular cells with equivocal TFF3 staining), to be reported with number of.
- Number and proportion of Cytosponge™ test results deemed insufficient/inadequate due to technical failure only
- Number and proportion of Cytosponge™ test results deemed low-confidence negative only
- Number and proportion of Cytosponge™ test results deemed equivocal only

The above measures will also be presented for first test only and for first and repeat test combined, excluding those patients receiving an inadequate test result but not attending their repeat test.

- 7) Endoscopy referral rates for 'adequate' test results and successful Cytosponge™ swallows:
- Proportion of positive Cytosponge™ patients out of all the ones with an adequate test result, both for first test only, and for first and repeat test combined
 - Proportion of positive Cytosponge™ patients out of all patients swallowing successfully a Cytosponge™ test, both for first test only, and for first and repeat test combined
- 8) Patient acceptability of Cytosponge™:

At first test:

- Number/proportion of patients invited who show interest
- Number/proportion of patients invited who receive screening phone call and how many of these are not eligible to have the test
- Willingness to have the test: number/proportion of patients invited who attend appointment
- Number/proportion of patients who fail to swallow
- Number of attempts to swallow per patient

At repeat test (in case of an 'inadequate' result at first test):

- Number/proportion of patients with an 'inadequate' first test result invited to a repeat test
- Number/proportion of patients with an 'inadequate' first test result interested or not interested in a repeat test
- Willingness to have repeat procedure: number/proportion of patients with an 'inadequate' test result who attend a second appointment
- Number/proportion of patients who fail to swallow
- Number of attempts to swallow per patient

All of these figures for first and repeat tests will be presented in a flowchart similar to the one used for the open Data Monitoring Committee (DMC) reports (see Section 10 for reference).

At baseline (before first test):

- Cancer worry and long-term emotional or physical harm as measured by STAI-6, a short-form of the state scale of the Spielberger State-Trait Anxiety Inventory
- Perceived risk of developing EAC: overall and compared to a person of the same age

At day 7-14:

- Cancer worry and long-term emotional or physical harm as measured by STAI-6
- Perceived risk of EAC: overall and compared to a person of the same age
- Test experience as measured by visual analogue scale (0 = "Completely unacceptable", 10 = "Completely acceptable")

- Test experience as measured by the Inventory To Assess Patient Satisfaction (5-point ordinal scale with 18 items)
 - Difference in STAI-6 scores at day 7-14 and baseline
- 9) Physician/nurse acceptability of Cytosponge™: assessed through qualitative interviews (not discussed in this document).
- 10) Safety of Cytosponge™:
See Section 8.
- 11) Performance of repeat Cytosponge™ test:
- Rate of conversion to an 'adequate' result after an 'inadequate' first test result = proportion of repeat tests that have an 'adequate' result, to report with number.
 - Number/proportion of repeat tests that have an 'inadequate' result.
 - Chances of a repeat test result being TFF3 positive (high or low-confidence) after a low-confidence negative result at the first test.

The measures above will be recalculated at a second stage excluding any patients invited to a repeat test and refusing to attend.

To be assessed using data from the usual care or *both* study arms:

- 12) Number of BE diagnoses missed in current management:
- Usual care arm: research endoscopy findings
- 13) Number of undiagnosed BEs in the general population vs in the group who received Cytosponge™:
- Intervention arm: research endoscopy findings
 - Usual care arm: research endoscopy findings
- 14) Acceptability of endoscopy:
- Intervention arm: number attending Cytosponge™ appointment
 - Usual care arm: number attending research endoscopies

Proportion of participants in the usual care arm who attend their research endoscopy invitation compared to proportion of participants in the intervention arm who attend their Cytosponge™ invitation.

- 15) Number of BE diagnoses for patients with a negative Cytosponge™ result:
- Intervention arm: research endoscopy findings
- Number of false negatives of the test and false omission rate.

- 16) Quality control of endoscopic and pathology results:

A central review by the study team of all endoscopic and pathology records of positive Cytosponge™ patients undergoing a confirmatory endoscopy will be performed. Its results will be compared to the endoscopic and pathology results of the study sites by quantifying the number of BE diagnoses missed, the number of any other malignant diagnoses missed and, if relevant, the number of BEs falsely detected. "True" PPVs will be calculated for overall results (first and repeat test combined).

A similar review will look into the results of research endoscopies for usual care and negative Cytosponge™ patients.

Epidemiological and longer-term objectives (for up to 10 years):

To be detailed in the BEST3 Epidemiological Analysis Plan.

Health economics analysis:

This is detailed in the BEST3 Health Economics Analysis Plan and will not be discussed here.

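### SAP Section 2.3 is inconsistent on which records may confirm the histological primary endpoint, and leaves room for confirmation that differs by arm

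*SAP*

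**What the plan says.** All of the following is in SAP Section 2.3, under the assessment of the primary endpoint, unless stated otherwise.

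- **Endpoint.** "The primary endpoint will be histological confirmed BE". It is reached by one of three routes: coded search with manual confirmation, manual case-note review, or NHS number linkage.
- **Further details.** "Where there is evidence of endoscopy from one of these sources, further details may be sought from clinical records". The next sentence adds: "Study-related endoscopies for participants with positive or other relevant Cytosponge™ results will be used for this purpose".
- **Manual review.** "All patients with a BE/OGD/EAC/upper GI referral should have a manual review to confirm the diagnosis". No distinction by arm is made. On histology: "The case-note review should make clear where the BE was confirmed on histology".
- **No review done.** For such flagged patients, "their BE status will be considered as (partially) missing and handled through multiple imputations".
- **Safeguard.** BE known to the study team but not found by one of the three routes is left out of the primary analysis. The stated reason: "This rule is to ensure that the same data collection methods are used in the two study arms". The SAP notes that usual care has no trial endoscopies.
- **Related sections.** Section 7.1.1 repeats the restriction to the three routes. Section 7.1.1.3 brings in diagnoses from confirmatory trial endoscopies as a sensitivity analysis.

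**The concern.** The safeguard governs how a case is *identified*. It does not say which records may *establish histology* once a patient has been flagged, and for a histology-only endpoint that second step decides whether the patient counts. The sentence on study-related endoscopies gives an intervention-only source a definite role at that point (*will*), while the general route to details is optional (*may*). Nothing limits that role to the sensitivity analysis.

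Take two patients whose GP notes show an endoscopy with an impression of BE but no pathology report. If the Cytosponge-positive patient's histology is taken from the study file, that patient counts. The usual-care patient counts only if somebody chose to look further. Two statisticians following the SAP could reach different case counts, and the difference would fall in one arm of a comparison where staff know the allocation.

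**Working it through.** **Step 1: reproduce the planned figures.** Inputs from Section 2.5.2: uptake 27%, BE prevalence 4%, Cytosponge sensitivity 85%, endoscopy in usual care 10%, BE among those endoscoped 6%, endoscopy sensitivity 100%.

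- Usual care: 0.10 × 0.06 = 0.600%.
- Intervention, Cytosponge route: 0.27 × 0.04 × 0.85 = 0.918%.
- Intervention, routine route: 0.27 × 0.15 × 0.006 + 0.73 × 0.006 = 0.0243% + 0.438% = 0.4623%.
- Intervention total: 1.3803%, the SAP's 1.38%. Planned ratio: 1.3803 / 0.600 = 2.30.
- With two-sided 5% and 90% power, the unrounded rates give 3382 per arm, or 6764, as stated. No sample-size figure is in question here.

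The Cytosponge route supplies 0.918 / 1.3803 = 67% of planned intervention-arm BE, so the way those cases are confirmed matters.

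**Step 2: upper scenario.** Let q be the share of routine-route BE with no histology in the GP notes. The SAP gives no value; 10% to 30% is an assumed range. Assume also that every Cytosponge-route case is confirmed from study files.

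Ratio(q) = [0.918 + 0.4623(1 − q)] / [0.600(1 − q)]

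| q | Intervention % | Usual care % | Ratio | Change |
|---|---|---|---|---|
| 0 | 1.380 | 0.600 | 2.30 | none |
| 10% | 1.334 | 0.540 | 2.47 | +7% |
| 20% | 1.288 | 0.480 | 2.68 | +17% |
| 30% | 1.242 | 0.420 | 2.96 | +29% |

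**Step 3: opposite scenario.** Suppose instead that study histology removes unconfirmed impressions in Cytosponge participants, while a share f of routine recorded BE stays in without confirmation.

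Ratio(f) = [0.918 + 0.4623/(1 − f)] / [0.600/(1 − f)]

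For f = 5%, 10% and 20% (assumed) this gives 2.22, 2.15 and 1.99.

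**Step 4: does the text favour one direction?** For a patient whose manual review is complete, Section 2.3 already treats an unconfirmed impression as no BE. A study file can then only add a case, which points upward. Step 3 needs unconfirmed routine BE to be counted. The histology rule excludes this for reviewed patients but is less explicit for BE found through linkage. Upward is the more natural reading, but it is not certain.

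**The case against.** The strongest reply is that histology is read in both arms by the same required step. Every flagged patient should have a manual review, and a missing review goes to multiple imputation rather than being counted as no BE. On this view the optional look-up is an extra, open to either arm. A study file cannot produce a primary case unless a GP or linked record has flagged the patient first, and Section 7.1.1.3 shows that trial-endoscopy data were meant for a sensitivity analysis.

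Most of this stands. A reader might infer that usual care depends wholly on optional details; the required review rules that out. It does not close the gap, for three reasons:

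- A review yields only what the GP record holds, and the list of review items in Section 2.3 does not name histology, although the text later expects the review to show it.
- Imputation covers reviews not done. A completed review without histology leaves the patient classed as having no BE.
- The sentence on study-related endoscopies sits under the primary endpoint with no limit on its use.

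A second reply concerns the remedy: one source for both arms restores 2.30 only if GP records hold histology equally often for trial and routine endoscopies. That is correct. If, for illustration, they held it for 70% and 90% respectively, the ratio would be (0.918 × 0.7 + 0.4623 × 0.9) / (0.600 × 0.9) = 1.96. The SAP itself expects trial-endoscopy cases to be the ones most often missed by the three routes.

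**Conclusion.** The point holds as an internal inconsistency that permits arm-dependent confirmation of the primary endpoint, so the rate ratio can be biased. A reader might go further and infer that the ratio *is* inflated. The SAP does not support that: it does not say that study files settle histology in the primary analysis, it gives no figure for missing histology, and a study record can refute a diagnosis as well as confirm one.

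Under the assumed ranges the planned 2.30 moves to between 1.99 and 2.96. The figures 2.47, 2.68 and 2.96 are an upper scenario, resting on an assumed q of 10% to 30% and on confirmation of every Cytosponge-route case from study files. The matter should be settled in the text before data lock.

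**What to change.** In Section 2.3, replace the two sentences on further details with a rule stating that:

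1. confirmation for the primary endpoint uses only the three named sources;
2. the same histology criterion applies in both arms;
3. for every flagged participant in either arm, the histology report *will* be requested through the practice;
4. the same rule applies in both arms when no report is obtained;
5. study-endoscopy files enter only the sensitivity analysis in Section 7.1.1.3.

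Report by arm the number of flagged cases with no histology available.

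**Cost.** Mainly wording, plus some report requests. These are subject to the existing data permissions, since Section 2.3 notes that only participants who accepted the Cytosponge invitation consented to use of their data. Some intervention cases may move from the primary to the sensitivity analysis. If 5%, 10% or 20% of Cytosponge-route BE were lost in this way with routine BE unaffected (assumed), the ratio would be 2.22, 2.15 or 1.99, and power at 6764 would fall from 90% to 87%, 83% or 74%. The sensitivity analysis keeps the fuller information.
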